We will select two sets of signal processing parameters that either provide a high level of signal manipulation (with concomitant improved audibility) (Fitting A) or a low level of signal manipulation (Fitting B). We will select signal processing (combinations of WDRC, frequency compression) that produce either high levels of signal manipulation or low levels of signal manipulation; that is, that represents a situation of more or less signal manipulation, with corresponding variability in patient response. Note that our goal here is simply to select processing choices that suit the experimental hypothesis; we are not interested in making recommendations about specific algorithm parameters (e.g., frequency compression); rather, we are interested in testing the idea that listeners respond differently to the net effect of signal manipulation and that those responses are related to patient factors including cognition. All hearing aid parameters will be constrained such that the signal is audible, comfortable, and clinically realistic (based on the range of available fitting parameters).

We will obtain hearing aids for use in the trial. We will choose the specific hearing aids based on the technology available at the time of the trial. Commercial hearing aids universally offer noise suppression and WDRC. We anticipate that twelve individuals (fit binaurally = 24 aids, with 4 aids held for backup) will be enrolled at a time. Each individual will wear one processing condition for 6 weeks, followed by the other for 6 weeks, for a total 12-week trial. Order of the processing conditions will be counterbalanced across subjects. Allowing for transition time (to order earmolds, program hearing aids, etc.) we anticipate testing 36 individuals per year and completing the target sample of 45 subjects in <1.5 years. Fitting procedure will follow accepted clinical protocol. Briefly, we will program each hearing aid to NAL-NL frequency-gain response, plus the desired features (e.g., frequency lowering, noise reduction, WDRC release time). Real-ear aided response will be measured with a probe microphone system and frequency-gain response adjusted to meet prescribed NAL-NL targets. Each

HA outcomes in Older Adults:

participant will be tested at the hearing aid fitting and again and 6 weeks post-fitting. During that time they will wear the hearing aids in their own environment.

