Outcome measures between the optimal and suboptimal conditions will be compared using a paired t-test. We expect customized processing settings, which will utilize our cognitive and peripheral test batteries, will result in statistically significant and clinically meaningful improvements when compared to traditional fittings. We will identify any acclimatization effects by monitoring changes in outcomes observed over time. All subjects are expected to fully acclimatize to the hearing aid device by the end of the six-week trial. We will use a paired t-test analysis to compare the outcomes between the “high modification” and “low modification” conditions. This experiment will be powered to detect mean differences of 0.5 standard deviations with a sample size of 45 at 90% power and $\alpha=0.05$.

Sharing of Results with Subjects

Results of standard clinical procedures (e.g auditory testing) will be made available to participants at their request. Participants often have questions about their hearing and hearing aids. Counseling and recommendations will be done by or under the supervision of [name] the study PI and clinical audiologist. If research participants request the results from the research testing or cognitive testing, these results will be provided to the participant with the explanation that they are for “research purposes only” and not meant as a diagnostic tool or clinically reliable.

Recruitment Methods

Individuals in our lab subject pool who have expressed an interest in future studies will be contacted by phone or email (whichever they have indicated as a preferred contact) by the PI or her research assistant. Additional subjects will be recruited as needed by: (a) Flyers posted in our clinic and on community bulletin boards (b) Letter to potential participants. These letters will be sent to potential participants in the Aging Research Registry and the Northwestern University Audiology Clinic (c) newspaper advertisements

Subjects will receive \$10 per hour for participation. Participants will receive a bonus payment of \$40 after 6 weeks of wearing Fitting A, and \$50 after 6 weeks of wearing Fitting B. Therefore in experiment 2, a subject will be paid \$250 if they complete all study visits/tasks. (8 study visits lasting 2 hours paid at \$10/hour: \$160 + bonus payments of \$40 and \$50 = \$250 total)The

HA outcomes in Older Adults:

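### The two-period crossover is compared with a paired t-test that ignores the assigned order; adding a period term would protect precision at almost no cost

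*Combined protocol and SAP*

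**What the plan says.** The Hearing aid fitting section describes a two-period crossover: "Each individual will wear one processing condition for 6 weeks, followed by the other for 6 weeks, for a total 12-week trial". It adds: "Order of the processing conditions will be counterbalanced across subjects". On assessments it says that each "participant will be tested at the hearing aid fitting and again and 6 weeks post-fitting".

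The Statistical analysis plan names one test, twice: "Outcome measures between the optimal and suboptimal conditions will be compared using a paired t-test", and later "We will use a paired t-test analysis to compare the outcomes between the" two modification conditions. The sample size statement is: "This experiment will be powered to detect mean differences of 0.5 standard deviations with a sample size of 45 at 90% power", at α = 0.05. On time effects the SAP says "We will identify any acclimatization effects by monitoring changes in outcomes observed over time" and "All subjects are expected to fully acclimatize to the hearing aid device by the end of the six-week trial".

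The covariates foreseen under Procedures Involved are pure-tone averages and the descriptive tests. Order and period are not among them.

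**The concern.** A paired t-test takes each participant's difference between fittings and disregards which fitting came first. If scores shift between periods, that shift enters the difference with one sign in one order and the opposite sign in the other. Counterbalancing cancels it in the mean but leaves it in the variance. The design therefore controls order, while the analysis gives up the precision that this control makes available.

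A period effect is plausible from the documents. Participants have not actively worn hearing aids in the past year, and they are tested repeatedly, so continued adaptation or practice with the test could move second-period scores. At stake are wider intervals, power below the stated 90% if the period effect is large, and a small bias if the two orders end up unequal.

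**Working it through.** **Inputs.** From the SAP: N = 45, effect 0.5 SD, α = 0.05, power 90%. From Hearing aid fitting: two periods, counterbalanced order, taken here as close to 1:1. Assumed:
- The test is two-sided.
- The 0.5 SD refers to the SD of the paired difference, which the SAP does not state.
- The period effect p (second minus first period, in the same SD units) is 0.1, 0.25, 0.5 or 1.0, because the documents give no value.

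**Step 1: the plan's own figure.** Noncentral t with 44 df and noncentrality 0.5 × √45 = 3.354 gives power of 90.66%. The stated 90% is reproduced when there is no period effect.

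**Step 2: what a period effect does to the paired t-test.** Write n₁ for the number wearing fitting A first, n₂ for B first, and n = n₁ + n₂. The A − B difference is shifted by −p in the first group and +p in the second. Then:
- bias of the mean difference = p(n₂ − n₁)/n
- expected variance of the differences = 1 + p² × 4n₁n₂/[n(n − 1)]

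At 22/23 and p = 0.5 the variance is 1 + 0.25 × 2024/1980 = 1.256, so the SD is 1.120. The 95% half-width is 2.015 × 1.120/√45 = 0.337.

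**Step 3: with a period term.** The estimate is the unweighted mean of the two order-specific mean differences. Its standard error is √[(1/n₁ + 1/n₂)/4] on n − 2 df, whatever p is. At 22/23 this is 0.149, the half-width is 2.017 × 0.149 = 0.301, and power is 90.62%. The width ratio is 0.337/0.301 = 1.12. With no period effect the term costs 90.66 − 90.62 = 0.04 point of power.

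**Step 4: power at N = 45, true effect +0.5 SD.** Paired-t power and type I error are simulated with 1,000,000 runs per cell. Width and type I error are for 22/23.

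| p | Paired t, 22/23 | Paired t, 23/22 | Period term | Width ratio | Paired-t type I error |
|---|---|---|---|---|---|
| 0.1 | 90.8% | 90.2% | 90.6% | 1.004 | 4.9% |
| 0.25 | 90.2% | 88.9% | 90.6% | 1.031 | 4.4% |
| 0.5 | 87.5% | 84.3% | 90.6% | 1.120 | 2.9% |
| 1.0 | 73.5% | 63.4% | 90.6% | 1.423 | 0.6% |

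At p = 0.5 the loss is 90.6 − 87.5 = 3.1 to 90.6 − 84.3 = 6.3 points. At p = 0.25 it is 0.4 to 1.7 points.

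**Step 5: 50 participants.** The Participants paragraph foresees two groups of about 25. At 25/25, paired-t power is 93.3%, 92.6%, 89.7% and 74.8% across the four values of p, against 93.4% with the term.

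**Step 6: unequal orders among completers.** Withdrawal of Subjects allows withdrawal and removal but gives no rate. If 5 of 50 are lost at random from 25/25 (assumed), the chance of a split of 24/21 or worse is 35%, and of 25/20 it is 5%.
- 24/21: the bias is 3/45 = 0.067p in size. At p = 0.5, paired-t power is 80.5% or 90.3% depending on direction, against 90.5% with the term.
- 25/20: the bias is 5/45 = 0.111p. At p = 0.5, paired-t power is 76.4% or 92.6%, against 90.3% with the term. Paired-t type I error is 4.9%, 4.7%, 4.0% and 2.1% across the four values of p.

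**The case against.** The case for leaving the plan alone is substantial. Order is counterbalanced, patient and speech tester are blinded, and with near-equal orders the paired t-test holds its error rate. The SAP expects acclimatization to be complete by the end of six weeks and will monitor change over time. The loss becomes material only when the period effect is about as large as the targeted treatment effect, and nothing in the documents points to one of that size. If about 50 participants complete in equal orders, a period effect of 0.5 SD still leaves 89.7% power.

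Most of this stands, and it sets the weight of the point: this is an efficiency gain. Three parts do not answer it. Monitoring change over time does not remove period variance from the treatment comparison. The acclimatization statement is an expectation, and it does not cover test practice. Equal orders at enrolment do not guarantee equal orders among completers.

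A reader might infer that every period effect costs power. The figures do not support that for unequal orders: with 20 wearing A first and 25 wearing B first, p = 0.5 raises paired-t power to 92.6%. That gain comes from bias in a favourable direction, so it is no argument for the paired test, but the loss of power is assured only with balanced order. The widening of intervals is general.

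**Conclusion.** The point holds as a low-cost improvement in efficiency. The SAP's only named comparison ignores the assigned order, so a period effect would widen intervals and, with balanced order, lower power. At N = 45 with near-balanced order the loss is under 2 points at p ≤ 0.25 SD. At p = 0.5 SD it is about 3 to 6 points, with 12% wider intervals. With unequal completers the estimate also absorbs a small part of the period effect, which can lower or raise power. These sizes rest on assumed period effects and on reading 0.5 SD as the SD of the paired difference.

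Two stronger readings are tempting and should be resisted. One is that the paired t-test is invalid here or produces false positives: its type I error is at or below 5% at every split from 22/23 to 25/20 for which it was computed. The other is that the stated 90% power is wrong: it reproduces, and it falls short only if a period effect exists and is large enough. Carryover is a separate matter that a period term does not address.

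**What to change.** In the Statistical analysis plan, replace both mentions of the paired t-test with one period-adjusted analysis. Suggested wording: *Each outcome will be compared between the high- and low-modification fittings with a linear mixed model with condition, period and sequence as fixed effects and participant as a random effect. Condition and period effects will be reported with 95% confidence intervals.*

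Comparing within-person differences between the two orders gives the same estimate, but only for participants with both periods. Because data collected before withdrawal may be used, the SAP should state which analysis is primary, and whether it is restricted to complete pairs or also uses participants with one period.

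The cost is SAP wording and one degree of freedom. If there is no period effect, the term costs 0.04 point of power at 22/23 and 0.4 point at 25/20 (90.7% to 90.3%). No participants, visits or data are added, because order is already assigned. For comparison, holding 90% power at p = 0.5 with the paired t-test and balanced order would take 52 participants. The reported period effect would also serve the SAP's own aim of identifying change over time.

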Outcomes. Two important goals in hearing-aid processing are to improve speech intelligibility and quality.

Speech intelligibility. Speech intelligibility will be tested using low-context (IEEE⁵¹) sentences in quiet and in babble at a range of signal-to-noise ratios (SNRs). The processing will be provided by the settings of the wearable hearing aids; and the patient will be aided binaurally. Subjects will be tested in a double-walled sound booth with the test signal (conversational speech level) presented through a speaker. The speaker will be positioned at a typical conversational distance (approximately 1m) and azimuth (0°) and the subject will respond by repeating the sentence heard. The hearing aid will be programmed by the research audiologist. Both the research assistant (who will conduct the speech tests) and the patient will be blind to the processing condition. Based on our previous data and on desire to sample realistic listening conditions we expect to use SNRs ranging from 0 to +10 dB. Our protocol for measuring speech intelligibility is as follows. The listener is seated in a double-walled sound booth and speech is presented to the listener at conversational levels in free field. Speaker distance (~ 1 m) and azimuth (0°) mimic a conversational situation. A locally-developed Matlab interface allows the listener to signal for presentation of the next sentence and for scoring of correct repetition of key words by an experimenter seated outside the sound booth. To confirm reliable scoring, an audio file of the listener's response is digitally stored and rescored by a second tester who is blinded to the initial scoring.

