Speech quality. There are many situations where speech intelligibility is high but sound quality is still rated as lacking. In addition, sound quality is a critical component to successful hearing aid outcomes. Quality ratings will therefore be obtained in addition to the intelligibility tests. Perceptual quality ratings will be obtained using a rating scale ranging from 1 (poor sound quality) to 10 (excellent sound quality). The rating scale will be implemented with a slider bar that registers responses in 0.05 increments. Listeners will make their selections from the slider bar displayed on the computer screen by using a customized interface that included a point-and-click method for recording and verifying rating scores. The timing of presentation will be controlled by the subject. This rating scale has been used successfully in quantifying the differential effects of hearing aid signal processing algorithms on sound quality ratings by both normal-hearing and hearing-impaired listeners.

Handicap reduction (subjective outcome). Objective measures provide insight into treatment efficacy, but effectiveness depends on the psychosocial adjustments to hearing loss that cannot be measured in a sound booth. Therefore self-administered scales are a critical component of assessing treatment effectiveness.

Three subjective measures will be used:

Effectiveness of Aural Rehabilitation (EAR). The EAR measures intrinsic issues of hearing loss (functional, physical, emotional, and social impairment), as well as extrinsic factors such as the comfort, convenience, and cosmetic appearance associated with hearing devices. Two modules, the "Inner EAR" (intrinsic) and the "Outer EAR" (extrinsic), were created. Both scales are brief (10 domain items, in

HA outcomes in Older Adults:

addition to one or two global questions). The EAR scales were developed and validated by the PI and colleagues. Item reduction was based on inter-item correlation, internal consistency, and factor analysis. Final scales take an average of 5 minutes to complete, have well-distributed responses, and no ceiling or floor effects. The effect size of the Inner EAR is high (2.1). The Minimal Clinically Important Differences (MCID) of the EAR is 6.0 points (on a 0 to 100 scale).

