Adherence. We will evaluate adherence using 2 questions: “Do you use your hearing aids?” and “How many hours a day do you use your hearing aid?” In our previous work, we used these questions and found responses to be well-distributed. While responses correlate with the Inner EAR ($r=.35$, $p<.001$) and satisfaction with amplification ($r=0.41$, $p<.001$), the moderate correlation coefficients suggest that adherence is an important construct that reflects more than mere function and satisfaction.

Speech and Spatial Qualities of Hearing (SSQ) questionnaire. The SSQ addresses static and dynamic listening environments, and includes situations with several types of background noise and where the target talker is unpredictable. The SSQ items are categorized as: understanding speech; judging sound location/distance; and sound clarity/naturalness. Patients rate how well they performed in the specified situation. The SSQ is included because we are interested in difficult listening situations which require cognitive resources, such as those involving background noise and multiple talkers. In a recent study²³ we collected SSQ data along with a variety of other objective measures, including ability to hear speech in complex noise. In those data, older listeners’ reports of listening in complex situations was much more variable than for younger listeners with comparable hearing thresholds.

Hearing aid use verification: Approximately one week after Fitting A, and one week after Fitting B participants will return to the lab to take the Practical Hearing Aid Skill Test (PHAST). This test requires participants to demonstrate hearing aid use tasks (e.g insertion/removal of hearing aid, changing batteries, and cleaning). This test insures participants are using and wearing their hearing aids appropriately.

Mid-fitting follow-up: Three weeks after hearing aid fitting participants will be contacted via telephone or email. The purpose of this follow-up is to insure participants are wearing their aids, and to assess any problems participants are having with the hearing aids.

Datalogging: During the one week post fitting verification and 6 weeks post fitting visit hearing aid data logs will be measured. This hearing aid feature allows the PI to identify how many hours the hearing aid has been in use.

Data Management

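### The plan compares its outcome measures (five are described) under one alpha of 0.05 and one 90% power figure, and names no primary outcome, testing order or multiplicity adjustment.

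*Combined protocol and SAP*

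**What the plan says.** The Statistical analysis plan is one paragraph. It states "Outcome measures between the optimal and suboptimal conditions will be compared using a paired t-test" and, a few sentences later, "We will use a paired t-test analysis to compare the outcomes between the" high- and low-modification conditions. It expects that customized settings "will result in statistically significant and clinically meaningful improvements when compared to traditional fittings". The power statement is "This experiment will be powered to detect mean differences of 0.5 standard deviations with a sample size of 45 at 90% power", with alpha 0.05. It names no outcome, does not say whether the test is one- or two-sided, and does not say which standard deviation is meant.

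The Outcomes section describes the measures:

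- It opens with "Two important goals in hearing-aid processing are to improve speech intelligibility and quality", and describes a test of each.
- Under Handicap reduction it adds "Three subjective measures will be used": the EAR, adherence and the SSQ. For adherence, "We will evaluate adherence using 2 questions".

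That makes five measures. None is called primary or secondary, and no order, gate or adjustment is given.

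**The concern.** The plan predicts statistical significance but does not say on which measure, or whether the 5% applies to each test or to the set. The single alpha and the single power figure therefore belong to no identified test. If significance on any one measure would be read as support for the prediction, the error rate for that overall conclusion exceeds that of a single test. No pattern of results is defined as a failure either. From these documents alone, a reader of the results could not tell a planned headline from one selected later.

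**Working it through.** **Inputs.** From the Statistical analysis plan: difference 0.5 SD, N = 45, power 90%, alpha 0.05, paired t-test. From Outcomes: five measures. Assumed: two-sided tests, one score per measure, one contrast, and equal correlations between the within-person differences. The documents do not give those correlations.

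**1. The plan's own figure.** Take 0.5 as the SD of the paired difference. The noncentral t has df = n − 1 and noncentrality 0.5 × √n.

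- n = 45: noncentrality 0.5 × √45 = 3.354, power 90.7%.
- Smallest n for 90% power: 44. The normal approximation, ((1.960 + 1.282)/0.5)² = 42.0, rounds up to 43.
- A one-sided test would need only 36, so two-sided is the matching reading.

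The planned 45 therefore reproduces as one two-sided test on one outcome.

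**2. Any false positive, no true differences, each test at two-sided 0.05.**

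- Five measures, independent: 1 − 0.95⁵ = 22.6%.
- Four measures (adherence kept only as a compliance check), independent: 1 − 0.95⁴ = 18.5%.
- Five measures, correlated (simulated paired t-tests, n = 45, 100,000 runs per setting): 20.4% at 0.35, 19.8% at 0.41, 18.6% at 0.5, 15.0% at 0.7, 10.4% at 0.9.
- Comparator for one test: 5%.

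**3. False positives in an expected direction only.** Each test contributes 0.025.

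- Five measures, independent: 1 − 0.975⁵ = 11.9%.
- Correlated: 10.3% at 0.35, 9.8% at 0.41, 5.1% at 0.9.
- Comparator for one test: 2.5%.

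This version suits optimal versus suboptimal, where improvement is predicted. It does not suit high versus low modification, for which the plan states no favoured direction.

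**4. Where 0.35 and 0.41 come from.** Both are reported under Adherence as correlations of scores in previous work, not of within-person differences. The 0.35 links adherence to the Inner EAR. The 0.41 links adherence to satisfaction with amplification, which is not one of the five measures. They are a rough guide only.

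**5. Power under the repair, at 0.5 SD of the paired difference.**

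- Primary at alpha 0.05, n = 45: 90.7%, unchanged.
- First Holm step over four secondary measures, alpha 0.05/4 = 0.0125: 76.9% with 45 completers, 70.5% with 40 (an assumed figure).

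**6. The SD wording.** If 0.5 were of the raw-score SD, the standardized difference would be 0.5/√(2(1 − r)), with r the within-person correlation (assumed). Power at n = 45 would be 64%, 79%, 91% or 99% at r = 0, 0.3, 0.5 or 0.7.

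**The case against.** The best reply is that the inflation depends on how the results are used. If the sponsor reports all five measures and claims nothing from a single success, each test keeps its 5%. The measures are probably correlated, adherence may be only a compliance check, and a primary outcome may be named somewhere outside these documents. All of that is fair. It is why the figures are conditional and shown over a range, with a four-measure case. It does not close the gap, because the plan predicts significance without saying what would count as achieving it. Even at correlation 0.9 the chance is about twice that of one test, on either way of counting.

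Four stronger readings are tempting, and the documents do not support them.

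- **The trial is underpowered.** The 64% figure needs a raw-score SD and no correlation between two scores from the same person. The paired-difference reading reproduces the plan without assuming a correlation, and the raw-score reading gives 99% at r = 0.7. The SD needs a clarifying phrase and is not shown to be a power problem. Nor do the documents forecast 40 completers. Procedures Involved plans about 25 participants in each of two working-memory groups, roughly 50, without saying how that relates to 45.
- **The two contrast labels double the number of tests.** Ten independent tests would give 1 − 0.95¹⁰ = 40%, but the text does not say that the labels denote different comparisons. This is a query.
- **The time point is missing.** Hearing aid fitting schedules testing at the fitting and at 6 weeks, and the plan adds "All subjects are expected to fully acclimatize to the hearing aid device by the end of the six-week trial". The 6-week visit only needs confirming as the analysis time point.
- **The emphasis was chosen after the results were seen.** Nothing in the documents shows this. They only leave a reader unable to rule it out.

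**Conclusion.** The point holds. The documents name no primary outcome, testing order or multiplicity rule, so alpha 0.05 and 90% power are valid for one test that the plan does not identify. The sample-size arithmetic itself is sound.

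If all five measures are tested unadjusted and any significant result is taken as support, the chance of at least one false positive is about 20% to 23% at correlations from 0 to 0.41 and about 10% at 0.9, against 5%. Counting only a predicted direction, it is about 10% to 12% and about 5%, against 2.5%. These figures rest on one score per measure, one contrast, two-sided tests and assumed equal correlations. The plan should be amended on this point. The SD and the contrast labels need clarification only.

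**What to change.** Before the outcome data are analysed by condition:

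1. Name one primary score for one contrast at the 6-week visit and test it at two-sided 0.05. The choice is the sponsor's and should match the study question. Hearing aid fitting asks whether response to signal manipulation relates to patient factors including cognition, and Procedures Involved forms working-memory groups. An overall high-versus-low comparison averages over those groups, so the plan should say how the primary test relates to them.
2. Attach the 90% power statement to that test only.
3. Make the other measures secondary with one score each, either Holm-adjusted or explicitly labelled unadjusted and supportive. For adherence, say which question is scored, since the first reads as yes/no and does not suit a paired t-test. Alternatively, list it as a compliance check outside the tested set.
4. Label sub-scores and results at single SNRs as descriptive.
5. As clarifications, state that the 0.5 SD is of the paired difference, and whether optimal/suboptimal and high/low modification mean the same contrast.

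If analysis by condition has already begun, which the documents do not say, report the choice of primary as made afterwards.

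**Cost.** Wording only. N stays at 45 and a single paired t-test as primary keeps its 90.7% power. With Holm over four secondary measures, first-step power falls to 76.9% with 45 completers, or 70.5% if 40 complete (assumed). Labelling the secondary measures supportive avoids that loss but gives up confirmatory claims on them.

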Prior to enrollment potential participants will have a hearing and cognitive test with authorization by a screening audiogram consent form. These tests will allow us to exclude potential participants from enrolling in the study who are ineligible based upon their hearing status or over-enrolling participants in a particular working memory group. If participant is eligible based upon their screening results, they will be enrolled in the study with separate consent. All subjects will provide their consent to study procedures to the investigator or her research assistants. This process will take place in the Hearing Aid Laboratory, prior to any research procedure taking place. All consent forms are stored in a locked file cabinet drawer within the Hearing Aid lab (a locked laboratory). An unlimited amount of time will be provided to the participant to ensure they have adequately reviewed the consent form and all questions have been addressed by study staff. Following the subject's opportunity to read the consent document, study staff will review each section with participant to clarify the study or any procedure, and ensure understanding. Additionally consent forms may be provided to a potential research participant before a study visit is scheduled so they may take extra time to review before committing to participation. All participants will receive a copy of their signed consent form.

Non-English Speaking Subjects

At this time we are unable to include non-English speaking subjects, because the study requires repetition of English-language materials.

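### Research test scores are released on request with no hold until the last outcome visit, so score-based expectations can influence the participant-reported outcomes of the second fitting (minor)

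*Combined protocol and SAP*

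**What the plan says.** The rule is in the combined protocol and SAP, under Sharing of Results with Subjects: "If research participants request the results from the research testing or cognitive testing, these results will be provided to the participant". The one condition is an explanation that the results are for research only and "not meant as a diagnostic tool or clinically reliable". That limits how the results are read, not when they are given. No other section defers release.

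The schedule is under Hearing aid fitting: "Each individual will wear one processing condition for 6 weeks, followed by the other for 6 weeks, for a total 12-week trial". On order, "Order of the processing conditions will be counterbalanced across subjects". On test times, each "participant will be tested at the hearing aid fitting and again and 6 weeks post-fitting".

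The blind is described under Outcomes, in the speech intelligibility paragraph: "Both the research assistant (who will conduct the speech tests) and the patient will be blind to the processing condition". The person who knows the setting is named there too: "The hearing aid will be programmed by the research audiologist".

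Sound quality (1 to 10 slider), EAR, SSQ and the two adherence questions are all answered by the participant. The Statistical analysis plan compares the two conditions by paired t-test.

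**The concern.** The trial relies on self-report to show effects that a sound booth cannot. Those answers are useful as separate evidence only if booth scores do not shape them. A participant told that one fitting gave the lower sentence score may judge that fitting more harshly, without knowing whether it is the high- or low-manipulation setting.

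The release rule leaves this possible. The second period begins after first-fitting scores exist. If testing at fitting applies to both fittings, scores under both exist from the first day of that period. The final subjective ratings come 6 weeks later. The same section notes that participants often have questions about their hearing and hearing aids, so requests are foreseeable, and staff have no written ground to defer one.

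At stake is a modest bias in the participant-reported comparisons. The planned paired t-test can neither detect nor remove it.

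**Working it through.** **1. The plan's own figure.** Inputs from the Statistical analysis plan: difference 0.5 SD, N = 45, 90% power, α = 0.05. I read the SD as that of the paired difference and the test as two-sided. From the noncentral t distribution with n − 1 degrees of freedom and noncentrality 0.5 × √n, N = 44 gives 90.0% power and N = 45 gives 90.7%. The stated figure reproduces. Changing when results are released affects neither N nor power.

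**2. Timeline.**

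| Time | Event | Scores a participant could request |
|---|---|---|
| Screening | Hearing and cognitive tests | No aided scores yet |
| Week 0 | First fitting, tested | First fitting |
| Week 6 | First fitting retested; second fitting begins | First fitting; also second, if tested when fitted |
| Week 12 | Second fitting retested; final ratings given | All |

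First-fitting scores precede the final ratings on any reading. Transition time between fittings would only lengthen the interval.

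**3. Does the bias cancel?** Call the fittings A and B. Suppose a share f of participants learn their scores before the final ratings, and knowing which fitting scored better moves the second-period rating by d (in SDs of the paired difference) towards the better-scoring fitting.

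- A scored better, order AB: B is rated d lower, so A − B rises by d.
- A scored better, order BA: A is rated d higher, so A − B rises by d.
- B scored better: A − B falls by d in both orders.

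If A scores better in a share p of participants:

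mean shift in A − B = f × [p × d − (1 − p) × d] = f × d × (2p − 1)

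Order drops out, so counterbalancing does not remove this shift. It vanishes only when p = 0.5. By contrast, a shift common to all second-period ratings, whatever the scores, does cancel under balanced order.

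**4. Illustration.** f, d and p are assumptions; the documents give none of them.

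| f | d | p = 0.5 | p = 0.6 | p = 0.75 | p = 1 |
|---|---|---|---|---|---|
| 10% | 0.3 | 0 | 0.006 | 0.015 | 0.03 |
| 20% | 0.5 | 0 | 0.02 | 0.05 | 0.10 |
| 40% | 0.5 | 0 | 0.04 | 0.10 | 0.20 |

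Example: 0.20 × 0.5 × (2 × 0.75 − 1) = 0.05 SD.

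**5. Effect on the test.** With no true difference, N = 45 and a two-sided 5% paired t-test, the chance of a significant result is 5.2% at a bias of 0.02 SD, 5.4% at 0.03, 6.2% at 0.05, 10.1% at 0.10 and 25.9% at 0.20. The last two need high values of all three assumed quantities together, or nearly so.

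**The case against.** **The blind is intact.** A reader might infer that releasing scores defeats the patient blind. The documents do not support that. The blind is to the processing condition; a score does not name the condition, order is counterbalanced, and nothing says that the setting or order is released with the results. This objection stands in full. What remains is an expectation effect, which is a weaker claim.

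**Reading span.** A reader might also infer that learning one's reading-span result mid-trial biases the comparison. Under Consent Process, "Prior to enrollment potential participants will have a hearing and cognitive test with authorization by a screening audiogram consent form", so the score predates both fittings. It is the same in both periods of a within-person comparison, and no section links order to it. I see no route to bias and make no claim about it.

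**Silence on timing.** The text does not require immediate release, and the consent form is not available to us. That is fair: a site could defer. But the rule is affirmative and gives staff no basis for deferring.

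**Little new information.** Quality, EAR, SSQ and use answers are the participant's own, and participants have some sense of how well they repeated the sentences. It is also not stated which measures are taken at which visit. This narrows the exposure mainly to the intelligibility score. It does not remove it, because a numerical comparison of two fittings is more than an impression.

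**Size.** f and d have no source in the documents, and a request rate near zero fits the text equally well. The trial's premise is that listeners respond differently, with low and high working-memory groups of about 25 each, so p may be nearer 0.5 than 1. This stands: for given f and d, the product f × d is a ceiling, not an expected value.

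**Objective measures.** Key-word scoring is rescored by a second blinded tester, and datalogging records hours of use. These are less exposed; the point concerns the participant-reported outcomes only.

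**Conclusion.** The concern holds in a limited form and is minor. The protocol allows a participant to learn aided intelligibility scores before giving the final quality, EAR, SSQ and use answers for the second fitting. The condition stays concealed. The risk is expectation based on scores, and it does not fully cancel under counterbalancing if one fitting scores better in most participants.

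No size can be established from the documents. The central illustration (f = 20%, d = 0.5) gives 0 to 0.10 SD as p goes from 0.5 to 1. The top of that range is a fifth of the 0.5 SD target (0.10 / 0.5 = 0.20). It rests on three assumed quantities and on the shift following the better-scoring fitting. With few requests or evenly mixed responses it is negligible. It is worth closing because the remedy is cheap and no later analysis can recover what expectation has altered.

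**What to change.** Amend Sharing of Results with Subjects, with matching consent wording, so that:

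- outcome-test scores (intelligibility, quality, EAR, SSQ) and the identity of the fittings are released only after the participant has completed, or left, the second 6-week assessment;
- earlier requests are logged and deferred to that point;
- results of standard clinical procedures, such as the hearing test, stay available on request as now.

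The cost is about one sentence in each document. Sample size, power and visits do not change. The downside is that a participant may wait up to about 12 weeks for results that the plan already labels as being for research purposes only. The log of requests would also show how often the question arises, which is the quantity f that the documents do not give.
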